3.4 Early Termination of the Study/Closure of the Research Center

The Sponsor has the right to terminate the Study at any time and the Sponsor and the Investigator have the right to close the Research Center at any time. This, of course, can only be carried out after mutual agreement. Termination of the study must be reported to the Institutional Review Board (IRB) and the Ethics Committee (EC). Upon early termination of the study or early closure of the research center, all study materials (except for documents that must be retained at the research center) must be returned to the sponsor. The investigator must retain other documents until notified of their destruction by the sponsor. Reasons for early termination of a trial or closure of a research center include, but are not limited to, the following reasons:

• New information leads to unfavorable risk/benefit judgments about the study drug, e.g., due to:

Protocol Version 3.0 Version Date: 25 Feb 2022

- lack of efficacy of the study drug, either in this or other studies; or
- other unfavorable safety findings, including clinical examination and non-clinical manifestations;
- In the opinion of the sponsor, continuation of the study is not justified for medical, ethical, or commercial reasons;
- It is unlikely that the study will be completed within an acceptable timeframe due to difficulties in enrolling subjects;
- Suspension or termination due to requirements of health/regulatory authorities.

3.5 End of study

Data lock and primary analysis will be performed 6 months after enrollment of the last subject. All subjects will continue to be followed up for an additional 6 months after the primary analysis as required by the protocol, i.e., the study will end 12 months after enrollment of the last subject, and a follow-up analysis will be performed at the end of the study. Subjects who have not yet experienced cGVHD progression at the end of the study, and in the judgment of the investigator, the benefits of continued dosing outweigh the risks, may submit a written request and, upon approval by the sponsor's Medical Director and documentation of the subject's willingness to continue the treatment, the sponsor will continue to provide BN101/belumosudil medication at no cost until cGVHD progression, intolerable toxicity, initiation of a new cGVHD therapy, recurrence of hematological neoplasm, loss to follow-up, withdrawal of consent, or death, etc., whichever occurred first. If, in the judgment of the investigator, there is no evidence of clinical benefit, withdrawal from the study is required. Subjects who remain free of disease progression at the time of withdrawal from the study or who withdraw from the study for reasons other than adverse events should have the dose of BN101/belumosudil tapered every 2 weeks as required by the protocol (e.g., 200 mg QD \rightarrow 200 mg QOD \rightarrow discontinue treatment).

Serious adverse events (SAEs), study drug use, and subject survival will continue to be collected for subjects who continue to be free of charge while the study drug, BN101/belumosudil, is administered at the end of the study.

The study will end when all subjects stop taking the study drug (Unless terminated earlier for the reasons set forth in Section 3.4).

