Data lock and primary analysis will be performed 6 months after enrollment of the last subject. All subjects will continue to be followed up for an additional 6 months after the primary analysis as required by the protocol, i.e., the study will end 12 months after enrollment of the last subject, and a follow-up analysis will be performed at the end of the study. Subjects who have not yet experienced cGVHD progression at the end of the study, and in the judgment of the investigator, the benefits of continued dosing outweigh the risks, the sponsor will continue to provide BN101/belumosudil medication at no cost until cGVHD progression, intolerable toxicity, initiation of a new cGVHD therapy, recurrence of

hematological neoplasm, loss to follow-up, withdrawal of consent, or death, etc., whichever occurred first; or will need to be withdrawn from this study if, in the judgment of the investigator, there is no evidence of clinical benefit.

Subjects who remain free of disease progression at the time of withdrawal from the study or who withdraw from the study for reasons other than adverse events should have the dose of BN101/belumosudil tapered every 2 weeks as required by the protocol (e.g., 200 mg QD \rightarrow 200 mg QOD \rightarrow discontinue treatment).

Subjects who completed or prematurely terminated study drug therapy entered a followup period in which the study center contacted subjects by telephone approximately every 12 weeks to confirm their survival, any changes in cGVHD therapy, and any antitumor therapy until no more subjects were taking study drug.

The safety assessment begins with the signing of informed consent form until 28 days after the last dose of study drug (unless otherwise indicated) and includes changes in physical examination, vital signs, laboratory tests, electrocardiograms, echocardiograms (if necessary), as well as adverse events, adverse events related to the study drug, and serious adverse events.

In addition, the study will evaluate the PK profile of BN101/belumosudil and its metabolites, m1 and m2, in all subjects, and the first 12 subjects will require intensive collection of PK blood samples. See Appendix (PK Blood Sample Collection Schedule and PK Blood Sample Collection Time Window) for PK blood sample collection.

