- The subject is discontinued due to an adverse event or serious adverse event that makes continuation of study drug treatment inappropriate; or the subject is discontinued due to an adverse event or serious adverse event for more than 14 days.
- The investigator determines that the subject's continued treatment with the study drug may pose a potential risk greater than benefit to the subject, including: pregnancy; enrollment in the study and discovery that the subject does not meet the study protocol inclusion criteria and that continued treatment with the study drug poses a risk greater than benefit to the subject; failure to follow the protocol or doctor's orders, unauthorized use of other treatments, or failure to take the medication in a timely manner and at a dosage that would interfere with the assessment of efficacy and increase potential safety risks.
- Subject withdraws informed consent/withdraws from the study.
- Subject lost to follow-up.

After discontinuation of study medication, subjects will undergo end-of-treatment visits and enter

a safety follow-up period (including a 28-day follow-up after the last dose and a long-term safety follow-up).

Subjects have the right to withdraw from the study at any stage of the study under the terms of informed consent, or to be "withdrawn" (or "dropped") from the study even if they do not explicitly withdraw from the study but no longer accept the study medication or the study evaluations. The reasons for withdrawal should be understood and documented to the extent possible, e.g., perceived intolerance of certain AEs associated with the study drug, other reasons for not being able to continue in the clinical study, or unexplained loss of visits.

(3) Treatment of withdrawn subjects

The investigator must complete the reason for the subject's withdrawal from the study on the electronic case report form (eCRF) and contact the subject to complete the evaluation program for the end-of-treatment visit (EOT) and safety follow-up (28 ± 7 days after the last dose of study drug or prior to initiation of a new treatment for systemic cGVHD) whenever possible, and keep records, documenting, whenever possible, the time of the subject's last dose of study drug. The eCRF should be retained for subjects who withdraw from the trial for whatever reason.

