4. STUDY DESIGN

4.1 Type of study and design rationale

Trial Design:

This study is a multicenter, open, single-arm phase II clinical trial to enroll 30 patients with

cGVHD who have undergone at least 1 but not more than 5 lines of systemic therapy, to evaluate the efficacy, safety, and PK characteristics of BN101/belumosudil in Chinese patients with cGVHD.

Subjects who sign an EC-approved ICF with confirmed screening eligibility will be enrolled to receive BN101/belumosudil (every 28-day cycle). Concomitant use of other cGVHD treatments (e.g., corticosteroids, CNI, MMF, sirolimus, and ECP) that had been stabilized in dose/regimen prior to screening was permitted during the study period, but initiation of new systemic cGVHD treatments was not permitted. Efficacy assessments were performed on Day 1 of Cycles 2 to 5 and every 2 cycles thereafter (i.e., Day 1 of Cycles 2, 3, 4, 5, 7, 9, 11, etc.). For subjects assessed as "Lack of Response -Mixed" and "Lack of Response - Progression" (See section 7.1.1, table 4), if the investigator believed that these subjects could continue to benefit from treatment with BN101/belumosudil, the treatment may be continued after a written application was submitted, and approval from the Sponsor's Medical Director as well as documentation of the subject's willingness to continue treatment was obtained. For subjects who did not achieve any response after 12 cycles of BN101/belumosudil treatment during the main study(the end of the main study is defined in section 3.5 of the main body), they should discontinue the investigational product treatment and withdraw from the study if they were judged by the investigator to have no clinical benefit (e.g., improvements in organ score, improvements in Lee symptom scores, reductions of corticosteroid/tacrolimus doses). Subjects who remain free of disease progression at the time of withdrawal from the study or who withdraw from the study for reasons other than adverse events should have the dose of BN101/belumosudil tapered every 2 weeks as required by the protocol (e.g., 200 mg QD \rightarrow 200 mg QOD \rightarrow discontinue treatment).

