4.3.6 Long-Term Safety Follow-Up

Subjects who terminate study treatment early before the end of the main study will be contacted by telephone by the study center approximately every 12 weeks to confirm their survival, any changes in cGVHD treatment, and any antitumor therapy until the end of the main study (see Section 3.5).

Subjects who have not yet experienced cGVHD progression at the end of the study, and in the judgment of the investigator, the benefits of continued dosing outweigh the risks, may submit a written request and, upon approval by the sponsor's Medical Director and documentation of the subject's willingness to continue the treatment, the sponsor will continue to provide BN101/belumosudil medication at no cost until cGVHD progression, intolerable toxicity, initiation of a new cGVHD therapy, recurrence of hematological neoplasm, loss to follow-up, withdrawal of consent, or death, etc., whichever occurred first. During this period, subjects will return to the study center in accordance with their clinical practice, and the study will continue to collect SAEs, study drug use, and survival (or can be contacted by phone). In addition, SAEs for this group of subjects will need to be collected up to 28 days (±7) after the last dose or the initiation of new cGVHD therapy.

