6.1 Dose Adjustment

Subjects who experience any clinically significant toxicity during treatment will need to be considered for suspension or termination of study drug therapy. Subjects who experience an AE related to study treatment may be dosed according to Table 3.

Table 3 BN101/belumosudil dose adjustment

Toxicity*	Dose Adjustment
≥ grade 3 hepatotoxicity (ALT/AST/TBIL)	 Suspend BN101/belumosudil administration; Within 14 days§toxicity does not return to ≤ Grade 1 or baseline level, then discontinue BN101/belumosudil therapy; Within 14 days§toxicity returns to ≤ Grade 1 or Baseline level, resume BN101/belumosudil administration at a reduced dose level [e.g., 200 mg QD → 200 mg once every other day (QOD)]; If the reduced dose level is administered for one full treatment cycle tolerated by the subject without recurrence of Grade 1 or greater hepatic function abnormality, return the dose to the original level for the following treatment cycle[e.g., 200 mg QOD → 200 mg QD]; If this toxic reaction recurs after the reduced dose level, terminate BN101/belumosudil treatment.
Other ≥ grade 3 clinically significant toxicity associated with BN101/belumosudil	 Suspend BN101/belumosudil administration; Within 14 days§toxicity does not return to ≤ Grade 1 or baseline level, then discontinue BN101/belumosudil therapy; Within 14 days§toxicity returns to ≤ Grade 1 or baseline level, then BN101/belumosudil administration is resumed at a reduced dose level [e.g., 200 mg QD → 200 mg QOD]; if the reduced dose level is administered for a full treatment cycle as tolerated by the subject, and there is no recurrence of Grade 1 or higher of this abnormality, then the next cycle of treatment the dose will be restored to the original level [e.g., 200 mg QOD → 200 mg QD]; If the toxic reaction recurs after administration at a reduced dose level, BN101/belumosudil treatment will be discontinued.

^{*} Severity of toxicity was determined according to NCI CTCAE v5.0.

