The study enrollment period is estimated to be 6 months. 6 months after the last patient enrollment, the database will be locked and the primary analysis will be conducted. After primary analysis, all patients will be followed up for additional 6 months and a follow up analysis will be conducted 12 months after the last patient enrollment.

Eligible patients who have signed informed consent will be enrolled to receive BN101/belumosudil (every 28-day cycle) until cGVHD progression, intolerable toxicity, initiation of a new cGVHD therapy, recurrence of hematological neoplasm, loss to follow-up,

withdrawal of consent, or death, whichever occurs first. During study, concomitant treatment with standard of care systemic cGVHD therapies such as corticosteroids, calcineurin inhibitors (tacrolimus, cyclosporine), sirolimus, MMF, or extracorporeal photopheresis (ECP), are permitted as long as the patient has been on a stable dose / regimen of these per the eligibility criteria. Initiation of new systemic cGVHD therapy while on study is not permitted. Response criteria will be assessed after cycles 1, 2, 3 and 4 and then after every other cycle thereafter (i.e. on Day 1 of Cycle 2, 3, 4, 5, 7, 9, 11 etc). For patients assessed as "Lack of Response - Mixed" and "Lack of Response - Progression" [Evaluated by the investigator based on the National Institutes of Health (NIH) Consensus Development Project on Criteria for Clinical Trials in cGVHD(2014), hereinafter referred to as the NIH Consensus Criteria (2014)], if the investigator believed that these patients could continue to benefit from treatment with BN101/belumosudil, the treatment may be continued after a written application was submitted, and approval from the Sponsor's Medical Monitor as well as documentation of the patient's willingness to continue treatment was obtained. For patients who did not achieve any response after 12 cycles of BN101/belumosudil treatment, they should discontinue the study medication and withdraw from the study if in the investigator's judgment there is no evidence of clinical benefit (e.g., improvements in organ score, improvements in Lee symptom scores, reductions of corticosteroid/tacrolimus doses). For patients whose cGVHD has not progressed at the time of discontinuation of the study treatment and who come off study for reasons other than AEs should be tapered off BN101/belumosudil by reducing the dose every other week (200mg QD → 200mg QOD → discontinue).

5. Study Endpoints

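### The Protocol's dose-taper rule joins its two conditions with an or where SAP section 4 has an and, so read literally it tapers progression-free subjects who leave because of an adverse event

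*Protocol*

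**What the plan says.** The Protocol states the taper rule three times, with the same connective each time.

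- Synopsis: "Subjects who remain free of disease progression at the time of withdrawal from the study or who withdraw from the study" for non-AE reasons are to be tapered.
- Section 3.5: the rule covers subjects without progression "at the time of withdrawal from the study or who withdraw from the study for reasons other than adverse events should have the dose" reduced in two-week steps.
- Section 4.1: the same sentence, "withdrawal from the study or who withdraw from the study for reasons other than adverse events should have the dose of BN101/belumosudil tapered".

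SAP section 4 (Study Design) applies the rule to those with no worsening of cGVHD, in these words: "at the time of discontinuation of the study treatment and who come off study for reasons other than AEs should be tapered off". The steps are again QD, then QOD, then stop.

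Other Protocol rules bear on stopping for an adverse event. Section 3.3 ends treatment at intolerable toxicity, and lists this ground for early termination: "The subject is discontinued due to an adverse event or serious adverse event that makes continuation of study drug treatment inappropriate". The opening of section 6.1 asks for suspension or termination to be considered for any clinically significant toxicity, with no grade limit. Table 3 then gives specific rules for hepatotoxicity of grade 3 or higher and for "Other ≥ grade 3 clinically significant toxicity associated with BN101/belumosudil". Its footnote requires withdrawal after a hold of more than 14 days. None of these mentions a taper, and no Protocol sentence exempts adverse-event exits from it.

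**The concern.** The phrase about reasons other than adverse events looks intended to keep subjects who leave because of toxicity out of the taper. Joined by an or, it cannot do that. Being progression-free is enough on its own, so the reason for leaving is never consulted for such a subject. The phrase then has only one effect: it adds progressed subjects who leave for non-AE reasons.

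Sites dose from the Protocol, not the SAP. A site following the sentence literally would give more drug to someone leaving because of an adverse event; a site following 3.3 or the evident intent would stop at once. With 30 subjects planned at roughly 6 to 9 centres, the same case could be handled differently. A taper would also move the date of last dose, from which the end-of-treatment visit and the 28-day adverse-event window are counted.

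**Working it through.** **Logic.** Let A = free of progression and B = leaving for a reason other than an adverse event. The Protocol tapers if A or B; SAP section 4 tapers if A and B.

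| Progression-free (A) | Non-AE reason (B) | Protocol | SAP |
|---|---|---|---|
| yes | yes | taper | taper |
| yes | no | taper | no taper |
| no | yes | taper | no taper |
| no | no | no taper | no taper |

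The Protocol tapers in 3 of 4 cells and the SAP in 1 of 4; they differ in 2.

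**First discordant cell (progression-free, AE exit).** This is the safety concern. It applies only to subjects still dosing when they stop. A subject withdrawn after a toxicity hold of more than 14 days is already off drug, so nothing remains to taper.

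**Second discordant cell (progressed, non-AE exit).** Section 3.3 allows treatment to continue after LR-M or LR-P with approval, so progressed subjects can still be dosing when they leave. The Protocol tapers them; the SAP does not.

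**Extra exposure in the first cell, per subject on QD.** The inputs are the 200 mg dose, the two-week step and the 28-day cycle, all from the Protocol. The Protocol does not say when the first reduction occurs, so two cases are shown as assumptions.

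- QOD starts at once: 14 days / 2 = 7 doses; 7 × 200 mg = 1,400 mg.
- Two more weeks of QD first: 14 + 7 = 21 doses; 21 × 200 mg = 4,200 mg.
- For scale, one QD cycle is 28 × 200 mg = 5,600 mg, so these are 1,400 / 5,600 = 25% and 4,200 / 5,600 = 75% of a cycle.

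A subject already on QOD would take no further doses if stopped at once, or about 7 (1,400 mg) if a two-week QOD step is given first.

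**With both conditions required in the Protocol,** only the first row of the table is tapered and the documents agree in all four cells.

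**The case against.** The best counter-argument is context. In 3.5 and the synopsis the sentence follows withdrawal for lack of clinical benefit; in 4.1 it follows the rule for non-responders after 12 cycles. These are non-AE exits. The stop rules in 3.3 and the opening of 6.1 have no grade limit, so a site would have to put a taper instruction above them to dose wrongly. This stands as evidence of intent, and it narrows the practical case. It does not cancel the rule as written, because none of those provisions says that the taper does not apply.

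A reader might go further in four ways that the documents do not support.

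- **That adverse events below grade 3, or unrelated ones, have no stop rule** because Table 3 has no row for them. The opening of 6.1 and the ground in 3.3 cover them. The example "perceived intolerance of certain AEs associated with the study drug" in 3.3 adds little: it illustrates why subjects choose to leave, and those refusing the drug are unlikely to take taper doses.
- **That 7 doses is a ceiling, or that a subject on QOD gets none.** Both depend on when the first reduction is made, which is not stated.
- **That the different reference times are a second fault of weight.** The Protocol looks at withdrawal from the study, the SAP at discontinuation of treatment. They can differ, since "Subjects who terminate study treatment early before the end of the main study will be contacted by telephone", but a subject already off drug has nothing to taper, so the difference is harmless.
- **That the sponsor meant to taper after adverse events, or that efficacy results are at risk.** The sentence's own wording and the SAP point away from the first; no endpoint definition depends on the taper.

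**Conclusion.** The inconsistency is real, stands in the current text of both documents, and is minor. It is most likely a drafting or translation slip. The Protocol should not leave an instruction that, taken literally, continues dosing in a progression-free subject who stops for an adverse event.

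The size rests on assumptions: about 1,400 mg to 4,200 mg extra for a subject on QD, depending on when the first reduction is made. This is what the literal reading would add for one affected subject, not an expected effect. The number of subjects concerned cannot be derived from the documents. No endpoint, analysis set or sample size changes.

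**What to change.** In the synopsis, 3.5 and 4.1, replace the sentence with wording such as: *Taper the dose every 2 weeks (e.g., 200 mg QD, then 200 mg QOD, then discontinue) in subjects who have not progressed when study treatment is discontinued and whose reason for discontinuing is not an adverse event.* This requires both conditions and takes the SAP's reference time.

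The edit changes both discordant cells, and the amendment should say so. Besides removing the taper after adverse-event exits, it ends the taper for progressed subjects who leave for other reasons, as SAP section 4 already has it. It would help to state in the same sentence when the first reduction is made.

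The cost is one sentence reworded in three places and a short memo to sites. No SAP edit, extra patients, visits or procedures are needed.

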4. STUDY DESIGN

4.1 Type of study and design rationale

Trial Design:

This study is a multicenter, open, single-arm phase II clinical trial to enroll 30 patients with

cGVHD who have undergone at least 1 but not more than 5 lines of systemic therapy, to evaluate the efficacy, safety, and PK characteristics of BN101/belumosudil in Chinese patients with cGVHD.

Subjects who sign an EC-approved ICF with confirmed screening eligibility will be enrolled to receive BN101/belumosudil (every 28-day cycle). Concomitant use of other cGVHD treatments (e.g., corticosteroids, CNI, MMF, sirolimus, and ECP) that had been stabilized in dose/regimen prior to screening was permitted during the study period, but initiation of new systemic cGVHD treatments was not permitted. Efficacy assessments were performed on Day 1 of Cycles 2 to 5 and every 2 cycles thereafter (i.e., Day 1 of Cycles 2, 3, 4, 5, 7, 9, 11, etc.). For subjects assessed as "Lack of Response -Mixed" and "Lack of Response - Progression" (See section 7.1.1, table 4), if the investigator believed that these subjects could continue to benefit from treatment with BN101/belumosudil, the treatment may be continued after a written application was submitted, and approval from the Sponsor's Medical Director as well as documentation of the subject's willingness to continue treatment was obtained. For subjects who did not achieve any response after 12 cycles of BN101/belumosudil treatment during the main study(the end of the main study is defined in section 3.5 of the main body), they should discontinue the investigational product treatment and withdraw from the study if they were judged by the investigator to have no clinical benefit (e.g., improvements in organ score, improvements in Lee symptom scores, reductions of corticosteroid/tacrolimus doses). Subjects who remain free of disease progression at the time of withdrawal from the study or who withdraw from the study for reasons other than adverse events should have the dose of BN101/belumosudil tapered every 2 weeks as required by the protocol (e.g., 200 mg QD \rightarrow 200 mg QOD \rightarrow discontinue treatment).

Data lock and primary analysis will be performed 6 months after enrollment of the last subject. All subjects will continue to be followed up for an additional 6 months after the primary analysis as required by the protocol, i.e., the study will end 12 months after enrollment of the last subject, and a follow-up analysis will be performed at the end of the study. Subjects who have not yet experienced cGVHD progression at the end of the study, and in the judgment of the investigator, the benefits of continued dosing outweigh the risks, the sponsor will continue to provide BN101/belumosudil medication at no cost until cGVHD progression, intolerable toxicity, initiation of a new cGVHD therapy, recurrence of hematological neoplasm, loss to follow-up, withdrawal of consent, or death, etc., whichever occurred first.

Serious adverse events (SAEs), study drug use, and subject survival will continue to be collected for subjects who continue to be free of charge while the study drug, BN101/belumosudil, is administered at the end of the study.

Subjects who have not terminated BN101/belumosudil treatment at the end of the main study will

have a uniform end-of-treatment visit at the end of the main study.

AEs that remain at the end-of-treatment visit will be subject to continued follow-up, and all SAEs and AEs related to study treatment will be subject to follow-up until the event is resolved and the investigator considers the event to be stabilized or irreversible.

Twelve subjects at the designated centers will receive dense PK blood collection and the remaining subjects will receive sparse PK blood collection.

The primary efficacy endpoint of the study was ORR, defined as the proportion of subjects evaluated as CR or PR according to the NIH Consensus Criteria (2014) at any one post-baseline assessment. Secondary efficacy endpoints included median Duration of Response (DOR), Change in Lee Symptom Scale Score, Response rate by organ system, Percentage of subjects with best efficacy as PR and percentage of subjects with best efficacy as CR, Change in corticosteroid dose, Change in CNI dose, Failure-Free Survival (FFS), Overall Survival (OS), Change in cGVHD severity based on the Physician-Reported Global cGVHD Activity Assessment, and Change in symptom activity based on cGVHD Activity Assessment Patient Self-Report.

Changes in the PROMIS Physical Psychological Functioning Global Health Score will be analyzed as an exploratory endpoint of this study.

If a subject withdraws early from the study, the withdrawn subject will not need to be replaced and will not be able to re-enter this trial.

